The solubility of M3814 is pH dependent; therefore, antacid drugs, H2-blocker and proton pump inhibitors (PPI) might affect absorption. PPIs should be stopped 5 days prior to the first treatment and avoided during the entire treatment period with study intervention. Antacid drugs should not be taken 1 hour before study intervention administration until 2 hours after study intervention administration. H2 blockers may be allowed but should be taken at least 2 hours after M3814 dose and stopped at least 6 hours before the next dose of M3814.

Any additional concomitant therapy that becomes necessary during the study and any change to concomitant drugs must be recorded in the corresponding section of the eCRF, noting the name, dose, duration, and indication of each drug.

If the administration of a nonpermitted concomitant drug becomes necessary during the study, e.g. because of AEs, suspension of the participant from treatment should be performed. The requirement to discontinue the participant from treatment should be discussed with the Sponsor. In case of discontinuation and where possible, the End of Treatment Visit and Safety Follow-up Visit and phone call 30 and 90 days after end of treatment should be performed as per Schedule of Activities (Table 1, Table 2, Table 3, and Table 4). Furthermore, in participants who discontinue from study intervention prior to disease progression tumor assessments should continue according to the Schedule of Activities until confirmed disease progression or start of a new anticancer treatment.

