In vitro studies suggest that CYP3A, CYP2C9, and CYP2C19 are involved in the metabolism of M3814. Using physiologically based PK modeling and simulation, potent inhibitors and inducers of CYP3A, CYP2C9, and CYP2C19 are predicted to have an influence on the PK of M3814. Therefore, foods (e.g. grapefruit and Seville oranges) or concomitant medications that are potent inducers or inhibitors of these enzymes should be used with caution. Participants will be instructed to avoid any intake of grapefruit, grapefruit juice, Seville oranges, Seville orange marmalade, or other products containing grapefruit or Seville oranges within 7 days before the first administration of the study intervention and during the study intervention administration.

The effect of M3814 on CYP3A-metabolized substrates is complex due to the time dependent inhibition and induction. It cannot be excluded that at high concentrations, M3814 affects the PK

of sensitive CYP3A substrates; therefore, sensitive CYP3A substrates with a narrow therapeutic index should also be used with caution and avoided if possible, during treatment with M3814. Drugs mainly metabolized by CYP2C9 with a narrow therapeutic index are to be used with caution and if possible, avoided during treatment with M3814.

The solubility of M3814 is pH dependent; therefore, antacid drugs and proton pump inhibitors might affect absorption (Section 6.5).

Drugs which are substrates of P-glycoprotein (P-gp) (e.g. dabigatran etexilate, digoxin), breast cancer resistance protein (BCRP) (e.g. rosuvastatin, sulfasalazine), or organic cation transporter 1 (OCT1) (e.g. metformin) with a narrow therapeutic index are to be used with caution. The Investigator may decide not to include a participant in the study, if the participant cannot be withdrawn from the drugs that have a narrow therapeutic index and that are known to be substrates of P-gp, BCRP, or OCT1; if the Investigator decides to enroll a participant who is treated with a drug that is known to be substrate of P-gp, BCRP, or OCT1 and has a narrow therapeutic range, close safety monitoring is advised.

The study will be performed in a study unit with direct access to a Hospital Emergency Unit. Equipment and medications, such as epinephrine and prednisolone equivalents, will be available at the study site for the treatment of emergencies.

Radiotherapy

Refer to Appendix 8 for details of RT.

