Within Part B of this study, a maximum delay of M3814 and/or RT up to and including 7 days in total is allowed within the complete treatment period. If RT and M3814 treatment have to be delayed by more than 7 days, the participant must be discontinued from study intervention unless the Investigator feels that the participant continues to achieve clinical benefit by continuing avelumab according to the study schedule, in this case the participant should be replaced for DLT assessment but could remain on the study and continue to receive monitoring according to the Schedule of Activities (Section 1.3).

If 50 mg QD is not tolerated, M3814 will be stopped. Any change from dosing schedule, dose interruptions, or dose reductions should be recorded in the eCRF.

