The total dose per selected site of 30 Gy will be given in 10 daily fractions of 3 Gy prescribed to the PTV with at least 95% of the PTV receiving 30 Gy. An acceptable variation is at least 90% of the PTV receiving 30 Gy. The maximum dose for any contiguous volume of no more than 0.03 cc inside the PTV must not exceed 120% of the prescribed dose. An acceptable deviation is a maximum dose inside the PTV of up to 125% of the prescribed dose. The minimum dose (0.03 cc) to the PTV volume should be no less than 27 Gy. All radiation doses will be calculated with inhomogeneity corrections.

Radiation Treatment Schedule

Localization, Simulation, and Immobilization for radiation treatment planning, as outlined in "Localization, Simulation, and Immobilization", will be performed no more than 35 days and no

less than 1 day before the first day of radiation treatment. The participant can initiate treatment any day of the week. Treatment will be delivered daily for 10 working days (generally Monday to Friday, with 2 days off [Saturday and Sunday]). Disruptions to the planned radiation treatment schedule should be avoided if at all possible. Any unexpected treatment break lasting > 2 days should be reported to the Investigator.

Table 21 Radiation Treatment Schedule

RT Planning Simulation	RT Treatment Day 1-5	RT Treatment Day 8-12	No. Fractions and Total Dose
Between Day -35 and Day -1	Week 1	Week 2	3 Gy per fraction per irradiated site for all participants
			To a total dose of 30 Gy in 10 fractions for each site
			Uniform dose prescription in all participants and uniform dose to all PTVs throughout the RT course

PTV=planning target volume, RT=radiotherapy.

Dose Calculations

All radiation doses will be calculated with inhomogeneity corrections that take into account the density differences within the irradiated volume.

Technical Factors

Beam Energy

Six- to 18-MV photons are recommended for non-superficial tumor targets; however, beam energy and type will be left to the discretion of the treating radiation oncologist in order to obtain the best dose distribution for the site being treated.

Beam Shaping

Multileaf collimation (MLC) or individually shaped custom blocks should be used to protect normal tissues outside of the target volume.

Localization, Simulation, and Immobilization

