- The participant will not be eligible if >10% of the total esophagus volume is estimated to receive more than 15 Gy (50% of the prescribed RT dose).

In general, acute RIE occurs typically 2 weeks after treatment begins and lasts until 4 weeks after treatment concludes, with progressively worsening odynophagia, nausea, dysphagia, and, if ineffectively managed, anorexia (Murro 2015; Baker 2016). Late RIE occurs more than 3 months after RT ends, with an average time from treatment to symptom onset of 6 months.

Radiation-induced esophagitis does not constitute a reason to interrupt or delay RT or the study interventions provided oral intake is sufficient to maintain hydration.

Radiation-induced esophagitis is treated symptomatically. Mild to moderate odynophagia is managed with topical analgesics such as oral viscous lidocaine (Berkey 2010; Sasso 2001). Treatment with nonsteroidal anti-inflammatory agents has been proposed. Reflux frequently associated with RIE can be treated with proton pump inhibitors or H2 receptor blocker and dietary modifications. Prophylactic antifungal agents are recommended due to a high incidence of thrush and candida esophagitis.

Participants should also be strongly advised to avoid alcoholic, acidic, or spicy foods or beverages during RT.

Radiation-Induced Lung Toxicity (RILT)

Common radiation lung toxicity includes radiation pneumonitis and fibrosis and pleural effusion.

Traditionally, RILT, which includes clinical radiation pneumonitis and clinical fibrosis should only be diagnosed after exclusion of infection, tumor progression, and other etiology for the clinical symptoms.

Several studies have evaluated the use of various drug therapies to mitigate radiation pneumonitis, but there are none outside of steroid therapy that are in routine use (Abratt 2002). Minimizing the volume of irradiated lung is particularly important as several studies have correlated dose and/or volume effects of RT with the risk of pneumonitis (De Ruysscher 2019).

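### Appendix 8 offers proton pump inhibitors for esophagitis reflux in Part B, but Section 6.5.3 tells sites to avoid them during treatment

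*Protocol*

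**What the plan says.** Protocol Appendix 8, under esophagitis, gives management advice for Part B: "Reflux frequently associated with RIE can be treated with proton pump inhibitors or H2 receptor blocker and dietary modifications". It attaches no time limit, no spacing from M3814 and no reference to the concomitant-medication rules.

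Protocol Section 6.5.3 (Prohibited Medicines) applies to all parts. On PPIs: "PPIs should be stopped 5 days prior to the first treatment and avoided during the entire treatment period with study intervention". For H2 blockers the rule is one of spacing: they "should be taken at least 2 hours after M3814 dose and stopped at least 6 hours before the next dose of M3814". The reason given is the pH-dependent solubility of M3814. Section 6.8 repeats it under M3814, noting that "antacid drugs and proton pump inhibitors might affect absorption".

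The two places also differ on what follows. If a nonpermitted drug becomes necessary, for example because of an adverse event, Section 6.5.3 says "suspension of the participant from treatment should be performed". Appendix 8 says "Radiation-induced esophagitis does not constitute a reason to interrupt or delay RT or the study interventions", provided oral intake keeps the participant hydrated.

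**The concern.** A site treating RIE reflux can follow Appendix 8 in good faith and prescribe a drug that Section 6.5.3 tells it to avoid. Two periods need to be separated.

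- **While M3814 is being given.** A PPI may alter absorption of the drug whose dose is being escalated, in cohorts of 3 to 6. SAP Section 8.1 lists receipt of an excluded concomitant medication among important protocol deviations. If the PPI starts before the tenth fraction day, the Day 12 profile and the accumulation ratio for Cmax (fraction day 10 over fraction day 1, SAP Section 16.1) could be affected.
- **After the last M3814 dose.** The absorption reason is gone, but the PPI sentence refers to study intervention generally, and in Part B that includes avelumab (SAP Section 8.2). Read literally, PPIs stay restricted while avelumab continues, and the suspension rule could hold avelumab for no pharmacological reason. Section 6.6.1 requires all three planned avelumab doses for a Part B participant to be evaluable for dose escalation.

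**Working it through.** The plan states no figure on this point. The check is a comparison of texts and a count of the dosing calendar.

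**Does any text reconcile the sections?** Section 6.5.2 permits supportive medicines only if the protocol does not exclude them, and its override covers emergencies. Routine reflux treatment fits neither. Appendix 8 does not point back to Section 6.5.3, and Section 6.5.3 makes no exception for RIE.

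**Can RIE treatment overlap M3814 dosing?**

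Inputs:
- Ten M3814 doses, given with RT on 5 days a week for 2 weeks (Section 4.1.1.2).
- Start day (Appendix 8): "The participant can initiate treatment any day of the week".
- Delay limit (Section 6.9.1): "a maximum delay of M3814 and/or RT up to and including 7 days in total is allowed within the complete treatment period".
- Typical acute RIE onset 2 weeks after treatment begins (Appendix 8): Day 1 + 14 = Day 15.

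Assumptions: fractions run Monday to Friday, M3814 is taken only on fraction days, missed fractions are made up on the next working days, and a 7-day delay means five missed working days.

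| Start | Fraction days, no break | Last dose, no break | One working day missed | Five working days missed |
|---|---|---|---|---|
| Mon | 1–5, 8–12 | Day 12 | Day 15 | 12 + 7 = Day 19 |
| Tue | 1–4, 7–11, 14 | Day 14 | Day 15 | 14 + 7 = Day 21 |
| Wed | 1–3, 6–10, 13–14 | Day 14 | Day 15 | Day 21 |
| Thu | 1–2, 5–9, 12–14 | Day 14 | Day 15 | Day 21 |
| Fri | 1, 4–8, 11–14 | Day 14 | Day 15 | Day 21 |

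For every start weekday, Days 1 to 14 hold exactly ten working days. The number of doses on or after Day 15 is therefore:
- No break: 0 of 10.
- One missed working day: 1 of 10.
- Five consecutive missed working days after fraction m (m = 1 to 9): the smaller of 5 and 10 − m. That is 5 of 10 for a break after fraction 5 or earlier, then 4, 3, 2 and 1 for a break after fraction 6, 7, 8 and 9.

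Delays are foreseen: Table 15 interrupts both M3814 and RT for Grade 3 or higher in-field mucositis or radiation dermatitis.

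**Is there a compliant option?** With once-daily M3814 the H2 spacing leaves 24 − 2 − 6 = 16 of 24 hours. A spaced H2 blocker satisfies both sections, though Appendix 8 does not mention the limit.

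**After the last M3814 dose.** Appendix 8 says acute RIE lasts until 4 weeks after treatment concludes, and avelumab is scheduled on Days 15 and 29. Most RIE reflux would therefore be treated when only avelumab remains, which is when the literal wording of Section 6.5.3 restricts PPIs without a reason.

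**The case against.** Appendix 8 presents its advice as examples, says reflux can be treated in several ways and directs no one to use a PPI. On that view the specific rule in Section 6.5.3 governs, and a careful site would use diet or a spaced H2 blocker. Silence on spacing is not permission to ignore it, and in Part B M3814 is taken at the site (Section 6.4), so spacing is easy to control. Section 6.5.3 words the PPI rule with *should*, and PPIs are not in its list of treatments that must not be given, so it is arguable whether the suspension rule applies to them. The suspension triggers also differ: one is the RIE itself, the other the need for a nonpermitted drug. The overlap is narrow, and eligibility already limits esophageal dose and excludes active esophagitis in the field. Finally, the protocol says only that absorption might be affected, without direction or size.

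Most of this stands as a limit on size. For H2 blockers the gap is a missing cross-reference that a site can resolve. The suspension clash depends on treating a PPI as nonpermitted, which its place under Prohibited Medicines supports but does not settle. Lower absorption is an inference from pH-dependent solubility. None of it removes the PPI mismatch: Appendix 8 names, without qualification, a class that Section 6.5.3 says to avoid, and a reader of the appendix alone has no warning.

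**Conclusion.** The concern holds and is minor. A PPI given under Appendix 8 before the last M3814 dose goes against Section 6.5.3. In a typical uninterrupted course no M3814 dose remains at RIE onset. One missed working day exposes 1 of 10 doses, and the maximum delay exposes 1 to 5 of 10. These counts rest on weekday fractions, make-up on the next working days, and onset at Day 15; earlier onset would widen the overlap. How often RIE reflux would be treated before the last M3814 dose cannot be derived from the documents, and neither can the effect on exposure. The purpose of the PPI rule points to M3814 dosing only, but its wording does not say so, which leaves PPI use during later avelumab treatment unclear.

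**What to change.** Make two wording changes.

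1. In the PPI sentence of Section 6.5.3, replace the reference to the treatment period with study intervention by *the M3814 treatment period*. In Part B, PPIs are then permitted after the last M3814 dose and do not trigger suspension as a nonpermitted drug.
2. In Appendix 8, after the reflux advice, add: *PPIs may be used only after the last M3814 dose; before then, H2 blockers follow the spacing in Section 6.5.3.*

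Nothing changes in Part A or Part FE while M3814 continues. The cost is one phrase and one sentence, with no extra participants, visits or procedures. Appendix 2 requires ethics approval before an amendment is implemented, so the changes are best included in the next planned amendment.

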6.5.3 Prohibited Medicines

Prohibited medicines include those listed in the exclusion criteria (Section 5.2).

- As stated in Section 5.2, chemotherapy, hormonal anticancer therapy with the exception of
 luteinizing hormone-releasing hormone analogs, biologic therapy, or any other anticancer
 therapy within 28 days of the first dose of study intervention administration (6 weeks for
 nitrosoureas or mitomycin C). These therapies are also prohibited during the treatment period
 (Part A, Part B, and Part FE) and up to 30 days after the end of RT (Part B).
- During the treatment period (Part A, Part B, and Part FE) and up to 30 days after the end of RT (Part B), chemotherapy, extensive RT (involving ≥ 30% of bone marrow) or any other anticancer therapy (biologics or other targeted therapy or investigational agent) and antineoplastic steroid therapy are also prohibited.
- Use of any other investigational treatments, or participation in any other interventional studies, during the entire study duration (Part A, Part B, and Part FE) is not permitted.

Furthermore, the following treatments must not be administered during the study:

- Immunotherapy, immunosuppressive drugs (i.e. chemotherapy or systemic corticosteroids) except:
 - When required for the treatment of irAEs or infusion-related reactions/hypersensitivity
 - Systemic corticosteroids at physiologic doses ≤ 10 mg/day of prednisone or equivalent
 - Systemic corticosteroids for management of participants with allergy to computed tomography (CT) IV radiographic contrast media.
- Administration of a live vaccine within 30 days of study intervention.
- Growth factors (e.g. granulocyte colony stimulating factor or granulocyte macrophage colony stimulating factor). Exception: Growth factors are allowed for treatment of study intervention-related myelosuppression and for prophylaxis of repeat myelosuppression after initial occurrence.
- Herbal remedies with immunostimulating properties (for example, mistletoe extract) or known to potentially interfere with major organ function (for example, hypericin).
- Medications or herbal supplements known to be strong inhibitors or inducers of CYP3A, CYP2C9, or CYP2C19.
- Drugs mainly metabolized by CYP3A or CYP2C9 with a narrow therapeutic index as judged by the Investigator (and after optional consultation with the Sponsor; for details see Special Precautions below; Section 6.8).

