6.9.2 Adverse Drug Reactions Requiring Avelumab Treatment Discontinuation or Modifications

Treatment with avelumab should be permanently discontinued, if any of the following ADRs occurs:

- Any Grade 4 ADRs:
 - Permanently discontinue avelumab except for laboratory values out of normal range that do not have any clinical correlate.
- Any Grade 3 ADRs:
 - Withhold avelumab except for laboratory values out of normal range that do not have any clinical correlate.
 - Permanently discontinue avelumab if toxicity does not resolve to Grade ≤ 1 or Baseline within 12 weeks of last administration or if the same Grade 3 toxicity recurs (consider consult with the Medical Monitor before permanently discontinuing the treatment).

If dosing is delayed more than 4 weeks, treatment may be resumed after consultation with the study Medical Monitor. Any delay in dosing in excess of 12 weeks is not permitted.

Infusion-related reactions and irAEs should be handled according to guidelines in Section 6.9.2.1.

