Supportive care may include antitussive therapy to suppress coughing, supplemental oxygen and treatment of comorbid diseases, such as chronic obstructive pulmonary disease or heart failure, which may contribute to symptoms. Moderate to high-dose steroid therapy is a common and effective therapeutic strategy that is generally given for a period of several weeks with a gradual taper as the symptoms settle (De Ruysscher 2019). However, steroids are minimally effective in the late consolidative phase of pneumonitis, when pulmonary fibrosis is well established (Abratt 2002).

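### Part B: the corticosteroid exceptions in Protocol 6.5.3 omit radiation toxicity, so the steroids that Appendix 8 describes for RT pneumonitis are, read literally, nonpermitted (minor conduct correction)

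*Protocol*

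**What the plan says.** Protocol 6.5.3 states that "the following treatments must not be administered during the study" and lists "Immunotherapy, immunosuppressive drugs (i.e. chemotherapy or systemic corticosteroids) except" in three situations. The first is "When required for the treatment of irAEs or infusion-related reactions/hypersensitivity". The second is a physiologic dose of at most 10 mg/day prednisone or equivalent. The third is allergy to CT contrast. If a nonpermitted drug becomes necessary, for instance because of an adverse event, the section says that "suspension of the participant from treatment should be performed" and that the need to discontinue should be discussed with the Sponsor.

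For RT toxicity, 6.9.3.1 points to local institutional guidelines and to Appendix 8. Under radiation-induced lung toxicity, Appendix 8 says of drug therapies for radiation pneumonitis that "there are none outside of steroid therapy that are in routine use". It adds: "Moderate to high-dose steroid therapy is a common and effective therapeutic strategy that is generally given for a period of several weeks". It also says the diagnosis "should only be diagnosed after exclusion of infection, tumor progression, and other etiology for the clinical symptoms".

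SAP 8.1 gives receipt of an excluded concomitant medication as an example of an important protocol deviation. It places the complete list in a separate Protocol Deviation Guidance document.

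**The concern.** The protocol expects this toxicity. Section 4.1.1.2 says lung toxicity may appear weeks to months after radiation, and gives this as the reason for the longer DLT period in Part B and for RT follow-up at 1, 3 and 12 months. Section 8.2 asks the investigator to separate causality between avelumab, M3814 and RT. An investigator who does so and settles on RT is left with two parts of the protocol that disagree. Appendix 8 describes moderate to high-dose steroids for several weeks, and 6.5.3 does not allow them.

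What is at stake is conduct. RT and M3814 are planned to end on Day 12, so a suspension for later pneumonitis falls in practice on avelumab. Care that the protocol itself describes could also be recorded as a deviation because of the cause named for the event.

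**Working it through.** No arithmetic applies. The check sets the passages side by side.

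| Question | Pneumonitis attributed to avelumab (irAE) | Pneumonitis attributed to RT |
|---|---|---|
| Treatment described | Table 17, Grade 2 and above: prednisone 1.0 to 2.0 mg/kg/day | Appendix 8: moderate to high-dose steroids for several weeks, then gradual taper |
| Status in 6.5.3 | Permitted by the first exception | No exception names it |
| Consequence for study treatment | Table 17: hold avelumab at Grade 2, stop permanently at Grade 3 to 4 | 6.5.3: suspend and discuss discontinuation with the Sponsor |
| Deviation status | None from the steroid | Possibly an excluded medication under SAP 8.1 |

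1. **Exceptions.** Section 6.5.3 lists three, and none names radiation toxicity. The dose exception does not help: it covers physiologic doses up to 10 mg/day, and a moderate to high dose is above that.
2. **General permission in 6.5.2.** The first bullet allows medication needed for the participant's welfare, but only if the protocol does not exclude it. Systemic corticosteroids are excluded.
3. **Rescue bullet in 6.5.2.** It allows rescue medication for anticipated adverse reactions, without naming steroids or radiation. Section 6.5.1, on rescue medicine, mentions corticosteroids only for infusion-related reactions. The bullet could be read to cover RT pneumonitis, but it does not clearly do so.
4. **Emergency sentence in 6.5.2.** It allows any medicine needed in an emergency and accepts that a deviation may result. A course of several weeks is not obviously an emergency measure.
5. **Deferral to local guidelines in 6.9.1 and 6.9.3.1.** This suggests that steroids were meant to be available. Neither section lifts the prohibition in 6.5.3.
6. **How far the suspension goes.** Section 7.1 requires withdrawal for a nonpermitted drug only where withdrawal is the predefined consequence. For steroids, 6.5.3 sets suspension and a discussion, not withdrawal.
7. **Reach into the analysis.** The DLT definition in 6.6.3 and the analysis sets in SAP 8.2 refer neither to concomitant medication nor to deviation status.

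**The case against.** The strongest reply is that the protocol, read as a whole, already permits these steroids. RT lung toxicity is anticipated, and the rescue bullet in 6.5.2, unlike the first bullet, is not limited to drugs the protocol allows. The sentence in 6.5.1 about corticosteroids says what must be on hand at the site and does not define rescue medicine. RT toxicity is expressly left to local practice. This is good evidence of intent. It does not settle the matter, because 6.5.3 states a prohibition with listed exceptions and nothing else clearly overrides it.

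The second reply is that the case is rare, and this stands. Part B plans 6 to 24 participants, of whom only some will have a thoracic target. Interstitial lung disease and prior pneumonitis are excluded, and lung dose is constrained. Other causes must be excluded before the diagnosis is made, so a suspected immune-related pneumonitis would start under the irAE exception. The gap opens only when the event is put down to RT and more than 10 mg/day is still needed.

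The third reply is that avelumab would usually be held on either route, and this also largely stands. Table 17 holds or stops it for immune-related pneumonitis from Grade 2, and 6.9.2 holds it for Grade 3 adverse drug reactions. At Grade 2, 6.9.2 sets no hold for an event attributed to RT, so the suspension in 6.5.3 is an added consequence there.

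A reader might also infer that a new rule for tapering steroids and resuming avelumab is needed. The documents do not support that. Limits already exist in 6.9.2 and Table 17, and the taper of at least 1 month in Table 17 is written for irAEs. Appendix 8 asks only for a gradual taper.

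**Conclusion.** The omission is real and should be corrected as a minor point of conduct. In Part B, the same steroid course is permitted if the pneumonitis is called immune-related and, read literally, nonpermitted if it is called RT-induced.

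The conclusion assumes that the exceptions in 6.5.3 are exhaustive and that the rescue bullet in 6.5.2 does not cover the case. The documents give no rate of steroid-treated radiation pneumonitis, so the number of participants affected cannot be stated.

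Three stronger readings are tempting and are not supported:

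- *The protocol blocks treatment of radiation pneumonitis.* It does not. Section 6.5.2 has its emergency sentence, and 6.5.3 has a route of suspension and discussion.
- *Each case is an important deviation.* SAP 8.1 makes that possible, but the complete list is in a guidance document that is not available here and may already deal with it.
- *The primary endpoint or the analysis populations are compromised.* Neither the DLT definition nor the set definitions depend on steroid use or deviation status.

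**What to change.** Add a fourth exception to the systemic corticosteroid item in 6.5.3: use required to treat radiation-induced toxicity in Part B.

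Leave avelumab handling to the rules already in the protocol, without a new taper rule:

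- The grade-based withholding in 6.9.2, including permanent discontinuation if a Grade 3 toxicity has not resolved to Grade 1 or Baseline within 12 weeks of the last administration.
- The delay limits in 6.9.2: "If dosing is delayed more than 4 weeks, treatment may be resumed after consultation with the study Medical Monitor", with 12 weeks as the maximum delay.
- The Table 17 row that stops avelumab when 10 mg/day or more of prednisone is needed for more than 12 weeks for reasons other than hormone replacement. That row sits in the irAE table.

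Once the exception is in 6.5.3, the steroid is no longer an excluded medication for SAP 8.1. The Protocol Deviation Guidance should be checked for consistency.

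The cost is one line of protocol text, with no added procedures, visits or participants.
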